#### **8.4.7 Day 27**

- Obtain vital signs (blood pressure, heart rate, respiratory rate, and body temperature).
- Collect blood for PK (24  $\pm$  4 hours after Day 26 dosing).
- Collect urine for PK (24  $\pm$  4 hours after Day 26 dosing).

- Review and record AEs and concomitant medications.

#### **8.4.8 Day 29 ( $\pm$ 1 Day)**

- Obtain vital signs and weight (blood pressure, heart rate, respiratory rate, and body temperature).
- Perform a brief, symptom-directed physical examination.
- Perform a single 12-lead ECG.
- Collect blood for the following:
  - Hematology;
  - Clinical chemistry;
  - Antibody analysis.
- Collect urine for urinalysis and pregnancy test (females).
- Perform physician assessment of keloid formation and volume.
- Assign mVSS and POSAS scoring ([Fearmonti et al 2010](#), see [Appendix D](#) and [Appendix E](#)).
- Photograph biopsy sites.
- Review and record AEs and concomitant medications.
- Note: Biopsy wound sites are to be photographed at the time the investigator suspects a keloid may be forming, at the time of observation of an unconfirmed keloid, and at the time of keloid confirmation.

#### **8.4.9 Day 36 ( $\pm$ 2 Days)**

- Obtain vital signs (blood pressure, heart rate, respiratory rate, and body temperature).
- Review and record AEs and concomitant medications.

#### **8.4.10 Days 57, 113, 141, 197, 225, 281, 309, 337 ( $\pm$ 7 Days)**

- Obtain vital signs (blood pressure, heart rate, respiratory rate, and body temperature).
- Perform physician assessment of keloid formation and volume.

- Assign mVSS and POSAS scoring ([Fearmonti et al 2010](#), see [Appendix D](#) and [Appendix E](#)).
- Review and record AEs and concomitant medications.
- Note: Biopsy wound sites are to be photographed at the time the investigator suspects a keloid may be forming, at the time of observation of an unconfirmed keloid, and at the time of keloid confirmation.

#### **8.4.11 Day 85 (± 7 Days)**

- Obtain vital signs (blood pressure, heart rate, respiratory rate, and body temperature).
- Perform a brief, symptom-directed physical examination (including documentation of weight).
- Collect blood for the following:
  - Hematology;
  - Clinical chemistry;
  - Antibody analysis.
- Collect urine for urinalysis and pregnancy test (females).
- Perform physician assessment of keloid formation and volume.
- Assign mVSS and POSAS scoring ([Fearmonti et al 2010](#), see [Appendix D](#) and [Appendix E](#)).
- Photograph biopsy sites.
- Review and record AEs and concomitant medications.

#### **8.4.12 Days 169 and 253 (± 7 Days)**

- Complete DLQI (Day 169 only).
- Obtain vital signs (blood pressure, heart rate, respiratory rate, and body temperature).
- Perform a brief, symptom-directed physical examination.
- Collect blood for the following:
  - Hematology;
  - Clinical chemistry;

- Antibody analysis (Day 169 only).
- Collect urine for urinalysis.
- Perform physician assessment of keloid formation and volume.
- Assign mVSS and POSAS scoring ([Fearmonti et al 2010](#), see [Appendix D](#) and [Appendix E](#)).
- Photograph biopsy sites.
- Review and record AEs and concomitant medications.

## 8.5 End of Study Visit (Day 365 ± 7 Days)

The end of study assessments will be performed on Day 365 ( $\pm$  7 days). For subjects who discontinue treatment early, the end of study assessments should be performed at the final study visit (assuming the subject has not withdrawn consent).

- Complete DLQI.
- Obtain vital signs (blood pressure, heart rate, respiratory rate, and body temperature).
- Perform a brief, symptom-directed physical examination (including documentation of weight).
- Collect blood for the following:
  - Hematology;
  - Clinical chemistry.
- Collect urine for urinalysis and pregnancy test (females).
- Perform physician assessment of keloid formation and volume.
- Assign mVSS and POSAS scoring ([Fearmonti et al 2010](#), see [Appendix D](#) and [Appendix E](#)).
- Photograph biopsy sites.
- Review and record AEs and concomitant medications.

## **9 ASSESSMENT OF SAFETY**

### **9.1 Specification of Safety Parameters**

Safety will be evaluated through continuous monitoring of AEs, vital signs, physical examinations, clinical laboratory measurements, and ECGs.

### **9.2 Definition of Adverse Events**

#### **9.2.1 Adverse Event**

An AE is any untoward medical occurrence whether or not considered drug related. An AE can be any unfavorable and unintended sign (e.g., an abnormal laboratory finding), symptom, or disease temporally associated with the use of a drug and does not imply any judgment about causality. An AE can arise with any use of the drug (e.g., off-label use, use in combination with another drug) and with any route of administration, formulation, or dose, including an overdose.

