**Main Criteria for Inclusion:**

1. Must provide written informed consent (signed and dated), and any authorizations required by law, and be able to comply with all study requirements.
2. Males or females,  $\geq 18$  years of age at the time of informed consent.
3. Females must have a negative serum pregnancy test at screening and a negative urine pregnancy test on their first dosing day.
4. Females must not be or planning to be pregnant or lactating during the study. Females must be post-menopausal (confirmed by follicle-stimulating hormone [FSH] test for subjects whose last menstrual cycle was within the last 2 years before screening), abstinent, in a monogamous same sex relationship, surgically sterile or, if of child bearing potential, must use two acceptable methods of contraception with at least one being a barrier method throughout their study participation and for at least 6 months following the last dose of study treatment. Acceptable methods of contraception include oral, injectable or implantable hormonal contraception, intrauterine device, or medically-confirmed vasectomized partner.
5. Males must be surgically sterile, abstinent, or if engaged in sexual relations with a female of child-bearing potential, must be using two acceptable methods of contraception with at least one being a barrier method for at least 6 months following the last dose of study treatment. Contraception for male subjects could include a condom and a highly effective second method during and for at least 6 months after the last dose of study treatment.
6. History of a high frequency of keloid formation (history of  $\geq 10$  keloids), or a history of large keloids ( $\geq 4$  cm) and Investigator feels that the subject is likely to form keloids in the upper back/shoulder area after punch biopsy.
7. Must have bilateral  $2\text{ cm} \times 2\text{ cm}$  areas, where skin punch biopsy may be performed in the upper back/shoulder region and can be covered by clothing, that are free of keloids, acne, striae or other skin pathologies or complications (e.g., tattoos, excessive hair) that may obstruct the ability to evaluate the biopsy sites.
8. Subject is currently clinically stable and is likely to remain clinically stable for a minimum of 14 months from screening.
9. Subject is not anticipated to require systemic corticosteroids during participation in the study.
10. Must be able to communicate effectively with study personnel.

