## 9.4 Collection and Reporting of Adverse Events

### 9.4.1 Initial Reporting of Adverse Events

Subjects will be evaluated and questioned generally to identify adverse events during the course of the study. Any events occurring prior to administration of the first dose of study treatment will be recorded on the Medical History eCRF. Events occurring after administration of the first dose of study treatment or those that increase in severity or frequency will be recorded as treatment-emergent AEs on the Adverse Event eCRF. Adverse events that occur up to and including 30 days after administration of the last dose of study treatment must be reported.

All AEs spontaneously reported by the participant and/or in response to an open question from study personnel or revealed by observation, physical examination, or other diagnostic procedures will be recorded on the Adverse Event eCRF. Any clinically relevant deterioration in laboratory assessments or other clinical findings, as assessed by the Investigator, is considered an AE and

must be recorded on the Adverse Event eCRF. In addition, an abnormal test finding will be classified as an adverse event if one or more of the following criteria are met:

- The test finding is accompanied by clinically significant symptoms.
- The test finding necessitates additional diagnostic evaluation(s) or medical/surgical intervention; including additional concomitant drug treatment or other therapy. Note: simply repeating a test finding, in the absence of any of the other listed criteria, does not constitute an AE.
- The test finding leads to a change in study treatment dosing or discontinuation of subject participation in the clinical research study.
- The test finding is considered an AE by the Investigator.

Wherever possible, a specific disease or syndrome rather than individual associated signs and symptoms should be identified. However, if an observed or reported sign or symptom is not associated with a documented disease or syndrome, the sign or symptom should be recorded as a separate AE. Laboratory data are to be collected as stipulated in this protocol. Clinical syndromes associated with laboratory abnormalities are to be recorded as appropriate (e.g., diabetes mellitus rather than hyperglycemia).

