### **11.4.3 Analysis of the Safety Endpoint: Safety and Tolerability**

#### ***11.4.3.1 Adverse Events***

The analysis of the safety endpoint will be based on AE incidence, physical examination findings, vital signs, ECG results and changes in clinical laboratory tests.

Adverse events will be coded by preferred term and system organ class using the Medical Dictionary for Regulatory Activities (MedDRA®) and summary tables for all AEs will be

generated for the FAS. Incidence rates and percentages will be summarized for each preferred term and system organ class. Additional summary tables will be generated for the following subsets: subjects with SAEs, subjects with related AEs, subjects with severe (Grade 3 or 4) AEs, and subjects who discontinue due to AEs. Depending on the doses achieved in this study, AEs may also be summarized by dose level. Severity, investigator-attributed relationship to study treatment, and action taken will also be recorded.

Concomitant medications will be coded using the World Health Organization Drug Dictionary (WHO-DD; 01 September 2017 or later version). A dictionary listing of all unique concomitant medications used in the study will be provided.

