#### ***11.4.3.2 Physical Examination***

Clinically significant changes in vital signs and new findings on physical examination will be recorded as AEs. Incidences of subjects with changes from normal physical examination findings at baseline to abnormal during the study may be generated.

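### The protocol does not say whether a keloid at a study wound is an adverse event, and its AE tables cannot separate the MRG-201 wound from the placebo wound

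*Combined protocol and SAP*

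**What the plan says.** Section 9.2.1 opens with "An AE is any untoward medical occurrence whether or not considered drug related" and continues: "An AE can be any unfavorable and unintended sign (e.g., an abnormal laboratory finding), symptom, or disease temporally associated with the use of a drug". Under section 9.4.1, AEs "revealed by observation, physical examination, or other diagnostic procedures will be recorded on the Adverse Event eCRF". Section 11.4.3.2 adds: "Clinically significant changes in vital signs and new findings on physical examination will be recorded as AEs". None of these sections mentions keloids or the study wounds, either to include or to exempt them.

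The Synopsis admits a subject where the "Investigator feels that the subject is likely to form keloids in the upper back/shoulder area after punch biopsy", and section 5.1 has the same criterion. Keloids are scored by mVSS, POSAS, volume and photography as pharmacodynamic assessments (section 7.4).

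On analysis, section 11.4.3.1 states: "Incidence rates and percentages will be summarized for each preferred term and system organ class". The tables use the FAS and may also be shown by dose level; no split by wound or side is mentioned. Sections 6.2.2 and 11.6.1 give every subject one MRG-201 wound and one placebo wound. Section 11.3.1 assigns safety data by actual treatment.

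The AE window is stated in two ways. Section 9.4.1 says: "Adverse events that occur up to and including 30 days after administration of the last dose of study treatment must be reported", and section 7.2.1 sets the same limit. Footnote i of Appendices A, B and C instead continues recording to the end of study visit when that falls later.

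**The concern.** The trial makes two wounds in people chosen because they are likely to form keloids there, so keloids should be common. With no rule, one investigator may enter a keloid on the AE form as a new examination finding, and another may treat it purely as efficacy data. With approximately 4 centers and about 12 subjects per cohort, the AE counts then depend partly on site habit.

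The larger statistical cost lies in the table. The design gives each subject an internal placebo control for anything that happens at a wound. A subject-level table with no wound split discards that control: an event at the placebo wound is counted in the same way as one at the MRG-201 wound. This matters beyond keloids. Section 2.1.3.2 reports that most MRG-201-related events in Phase 1 were injection site erythema or edema, so local events are where a drug effect is most likely to appear. Section 11.5 justifies the sample size on safety alone.

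**Working it through.** There is no stated figure to reproduce, because the plan sets no power, alpha or keloid rate. The check has three parts.

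**1. Do the tables separate the wounds?** Each subject's actual treatment is both MRG-201 and placebo, so classifying subjects by actual treatment puts all of them in one group. Preferred term and system organ class do not identify the wound, and no section requires the wound side of a local AE to be recorded. The investigator's causality call does not fill the gap: investigators are blinded (section 11.6.1), and the all-AE table is not filtered by causality.

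**2. How much of the keloid outcome can enter under each window?** Nominal days are used throughout, ignoring visit tolerances. Under sections 7.2.1 and 9.4.1, the window ends on the day of the last dose plus 30. A second cycle may start from Day 29 to Day 85, and its last dose comes 11 days after its first.

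| Regimen | Last dose | Window ends |
|---|---|---|
| 6 doses, one cycle | Day 12 | 12 + 30 = Day 42 |
| 12 doses, one cycle | Day 26 | 26 + 30 = Day 56 |
| Second cycle begun Day 29 | 29 + 11 = Day 40 | Day 70 |
| Second cycle begun Day 85 | 85 + 11 = Day 96 | Day 126 |

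Confirmation by persistence takes 12 weeks (84 days) from a first mVSS of 3 to 5. A scar first scored in that range on Day 8 reaches 8 + 84 = Day 92, and the next monthly visit is Day 113. Keloids confirmed this way fall outside the window after a single cycle, and can fall inside only after a late-started second cycle. The 24-week endpoint (Day 169) is outside every row of the table.

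Early entry remains possible. In the 6-dose regimen mVSS is scored on Days 8, 12, 19 and 29, and a total of 6 or more with a height score of at least 1 confirms a keloid at once. On the Appendix D scale, red (2) + firm (3) + under 2 mm (1) = 6. Early unconfirmed scars could also be recorded.

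Under footnote i the window runs to Day 365, so every confirmed keloid at either wound could enter.

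**3. Size under the longer window.** The documents give no keloid rate, so the placebo-wound rate p is assumed to lie between 0.30 and 0.90, with 12 subjects and every keloid recorded as an AE at every site.

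- No keloid at any MRG-201 wound: 12 × 0.30 = 3.6 to 12 × 0.90 = 10.8 subjects with a keloid AE, all of them MRG-201-treated.
- Same rate at both wounds, independent: 1 − (1 − p)² gives 1 − 0.70² = 0.51 to 1 − 0.10² = 0.99, or 6.1 to 11.9 of 12 subjects.
- First case, but only one site of 4 records keloids (12 / 4 = 3 subjects): 3 × 0.30 = 0.9 to 3 × 0.90 = 2.7 subjects.

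These are counts of subjects with a keloid AE. The any-AE total rises by less wherever such a subject already has another AE.

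**The case against.** A reader might infer that the rules make every keloid, or even every scar, an AE that must be recorded. The documents do not support that. They are silent, and the second sentence of section 9.2.1 speaks of an event that is unfavorable and unintended. Whether a keloid anticipated at enrollment meets that is left to the investigator. An ordinary scar is the unavoidable result of the punch biopsy the protocol itself performs, and is not clearly untoward. Nor does triamcinolone settle it: the criterion in section 9.4.1 on added treatment concerns a test finding that makes treatment necessary, whereas triamcinolone is optional.

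Four further points can be made for the plan.

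- The 30-day rule keeps out the 24-week endpoint and most confirmed keloids. This stands if that rule governs, but footnote i contradicts it, and AEs are reviewed and recorded at every visit to Day 365.
- Section 9.3.1 directs events explained by an underlying condition to the not-related class, so a low-grade keloid judged unrelated would not enter the related, severe, serious or discontinuation subsets. This stands for those subsets. It does not protect the any-AE and system-organ-class totals.
- Keloids would form an identifiable preferred-term row, so a careful reader could discount them. This stands, but the row would not show which wound was involved.
- The eCRF Completion Guidelines (section 12.2) and the planned separate SAP (section 11.1) may supply a rule. Neither is in the document, so this cannot be judged.

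A rule keeping uncomplicated keloids off the AE form would also be open to objection, because it could hide drug-related worsening at the MRG-201 wound.

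**Conclusion.** The point holds as an unresolved ambiguity combined with a table that cannot attribute local events. The AE rules can cover a study-wound keloid, no section says whether they do, and any local event recorded from the placebo wound counts in the any-AE and system-organ-class totals of MRG-201-treated subjects.

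The figure of up to 3.6 to 10.8 of 12 subjects rests on an assumed placebo-wound rate of 30% to 90%, the end-of-study window, and full recording at every site. Under the 30-day window the effect is far smaller, limited mainly to early scars and early keloids with an mVSS of 6 or more. A reader might conclude that an ineffective drug would also look unsafe. That goes too far, since only the pooled totals are inflated and the keloid row would be visible. The loss of the within-subject placebo comparison for local AEs does not depend on the keloid rate or on the choice of window.

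**What to change.** - **Section 9.4.1:** state one rule for all sites on whether a keloid at a study wound is recorded as an AE.
- **AE eCRF:** record the wound side for every local AE.
- **Section 11.4.3.1 and the SAP:** tabulate local AEs by wound, MRG-201 against placebo. Show any study-wound keloid recorded as an AE by wound and apart from the pooled incidence totals, without suppressing its reporting.
- **AE window:** reconcile sections 7.2.1 and 9.4.1 with footnote i of Appendices A, B and C.

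The cost is one extra eCRF field, one extra table or listing, and a short text change. The by-wound table needs no additional assessments.

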#### **9.2.2 Suspected Adverse Reaction**

A suspected adverse reaction is any AE for which there is a reasonable possibility that the drug caused the AE. For the purposes of Investigational New Drug (IND) safety reporting, “reasonable possibility” means there is evidence to suggest a causal relationship between the drug and the AE. Suspected adverse reaction implies a lesser degree of certainty about causality than adverse reaction, which means any AE caused by a drug.

#### **9.2.3 Life-Threatening AE or Life-Threatening Suspected Adverse Reaction**

An AE or suspected adverse reaction is considered “life-threatening” if, in the view of either the Investigator or Sponsor, its occurrence places the subject at immediate risk of death. It does not include an AE or suspected adverse reaction that, had it occurred in a more severe form, might have caused death.

#### **9.2.4 Serious AE or Serious Suspected Adverse Reaction**

An AE or suspected adverse reaction is considered “serious” if, in the view of either the Investigator or Sponsor, it results in any of the following outcomes:

- Death.
- A life-threatening AE (see [Section 9.2.3](#)).
- Requires prolongation of existing hospitalization.

- A persistent or significant disability or incapacity or substantial disruption of the ability to conduct normal life functions.
- A congenital anomaly/birth defect.
- Important medical events that may not result in death, be life-threatening, or require hospitalization may be considered serious when, based upon appropriate medical judgment, they may jeopardize the subject and may require medical or surgical intervention to prevent one of the outcomes listed in this definition. Examples of such medical events include allergic bronchospasm requiring intensive treatment in an emergency room or at home, blood dyscrasias or convulsions that do not result in inpatient hospitalization.

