## 4 STUDY DESIGN

This is a double-blind, placebo-controlled, multi-center, outpatient exploratory efficacy study in subjects with a high likelihood of keloid formation (i.e., history of  $\geq 10$  keloids or history of large keloids,  $\geq 4$  cm), with MRG-201 and placebo administered by intradermal injection around the site of two separate punch biopsies.

A minimum of 12 subjects are anticipated for enrollment in the first cohort of the study to attain at least 10 subjects who complete study participation through 24 weeks after excisional wound creation. Subjects who drop out for reasons other than safety or study treatment tolerability may be replaced with sponsor approval (up to 16 total including replacements). The sponsor may enroll up to 5 additional cohorts of 12 to 16 subjects each (up to 80 total additional subjects) to assess lower doses and/or regimens.

Subjects in the initial cohort will undergo a screening period lasting up to 28 days, followed by a double-blind, 12-day active treatment period (first cycle of study dosing) conducted in the outpatient setting, a possible second 12-day cycle of study dosing as outlined in [Section 4.2](#), and a follow-up period of up to 52 weeks ( $\pm 7$  days) after initiation of the first cycle of study dosing. Subjects in additional cohorts may receive lower doses or an extended 26-day active treatment period without the option to receive a second cycle of treatment. Follow-up periods for those additional cohorts will remain unchanged.

Subjects will be continuously monitored for safety through evaluations of AEs, vital signs, physical examination findings, clinical laboratory measurements, and ECG monitoring.

Samples will be collected for plasma PK on Days 1, 2, 12, and 13 (or Days 1, 2, 26, and 27 for subjects receiving an initial 26-day treatment cycle).

The punch biopsy wound sites will be evaluated for keloid formation, photographic assessment, and clinical response during the active treatment and follow-up periods of the study. Biopsy

samples will be saved for future protein and/or nucleic acid analysis to assess MRG-201 effects in subjects who form keloids.

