## **7.2 Safety Assessments**

### **7.2.1 Adverse Events**

AEs will be assessed at each study visit by direct observation and subject interviews. The severity of AEs will be evaluated using the NCI CTCAE, version 5.0. All AEs that occur from initiation of study treatment through 30 days after the last dose of study treatment must be recorded, regardless of causal assessment to study treatment.

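### Section 9.2.4 leaves new inpatient admission out of the SAE criteria, so in this outpatient trial an admission that meets no other criterion is serious only by discretion

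*Combined protocol and SAP*

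**What the plan says.** Section 9.2.4 calls an event serious if, "in the view of either the Investigator or Sponsor, it results in any of the following outcomes", and then gives six bullets: death; a life-threatening event; "Requires prolongation of existing hospitalization"; persistent or significant disability or substantial disruption of normal life; congenital anomaly; and important medical events. The last bullet reads in part "or require hospitalization may be considered serious when, based upon appropriate medical judgment", and asks whether the event "may require medical or surgical intervention to prevent one of the outcomes listed in this definition". Its examples are events treated without inpatient admission.

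Section 4 describes the setting: "This is a double-blind, placebo-controlled, multi-center, outpatient exploratory efficacy study". SAE incidence is part of the safety endpoint (3.2.1). Section 11.4.3.1 gives SAEs their own table: "Additional summary tables will be generated for the following subsets: subjects with SAEs". Section 9.5.1 requires an SAE to be reported to the sponsor within 24 hours of awareness.

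On timing, Section 7.2.1 says "All AEs that occur from initiation of study treatment through 30 days after the last dose of study treatment must be recorded". Section 9.4.1 (reporting of AEs) and 9.5.1 (the SAE report) use the same 30 days. Section 7.2.1 also says "AEs will be assessed at each study visit by direct observation and subject interviews". The visit lists in Section 8 order AE review and recording through Day 365. Footnote i of Appendix A, h of Appendix B and i of Appendix C record all AEs, including SAEs, to the later of 30 days after the last dose and the end-of-study visit.

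**The concern.** The definition contradicts itself. Its last bullet makes sense only if admission is already a criterion, yet the list contains no such criterion. No other section supplies one.

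Read literally, a subject admitted from home has no existing stay to prolong, so the hospital bullet cannot apply. Seriousness then rests on judgment, and two sites could classify the same admission differently. At stake are the 24-hour report and the SAE count, in a trial with no study-specific committee (Section 10) and no formal stopping rules (9.8).

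The 30-day wording is a lesser matter. Sites should not have to work out how it fits with the longer recording period in the appendices.

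**Working it through.** The plan states no figure to reproduce. The check compares the texts, followed by simple arithmetic.

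**1. A new admission against each criterion in 9.2.4**

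| Criterion | Met by a new admission as such? |
|---|---|
| Death | No |
| Life-threatening | No; 9.2.3 requires immediate risk of death |
| Prolonged existing stay | No; there is no stay to prolong |
| Disability or substantial disruption | Not by itself; depends on the case |
| Congenital anomaly | No |
| Important medical event | Only by judgment |

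**2. The last bullet.** It is permissive, and it is framed around events that may fall short of admission. Its test is whether intervention may be needed to prevent a listed outcome, and new admission is not listed. The result is odd. Allergic bronchospasm treated intensively in an emergency room is a named example of a possibly serious event, while the same event leading to admission meets no listed hospital criterion.

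**3. Size.** Inputs are the cohort size of 12 to 16 and the maximum of 96 subjects (synopsis). One admission classified one way or the other changes SAE incidence by 1/12 = 8.3, 1/16 = 6.3 or 1/96 = 1.0 percentage points. No expected admission rate is given, so the number of affected events cannot be estimated.

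**4. Secondary point: the windows.** Inputs are last dose on Day 12 or Day 26 (6.2.1); last dose of a second cycle 11 days after its start (4.2), with the start assumed at the Day 57 or Day 85 visit; and end of study on Day 365. The 30-day limit is last dose + 30. A visit is counted as late if the whole of its ±7-day window lies after the limit.

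| Regimen | 30-day limit | Days to Day 365 | Late visits |
|---|---|---|---|
| Six doses | 12 + 30 = 42 | 365 − 42 = 323 | 12 (57 − 7 = 50 > 42) |
| Twelve doses | 26 + 30 = 56 | 365 − 56 = 309 | 11 (50 < 56, so the Day 57 visit can fall on either side) |
| Second cycle from Day 57 | 57 + 11 + 30 = 98 | 365 − 98 = 267 | 10 (113 − 7 = 106 > 98) |
| Second cycle from Day 85 | 85 + 11 + 30 = 126 | 365 − 126 = 239 | 9 (141 − 7 = 134 > 126) |

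These figures show only where the texts differ. They do not estimate lost events.

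**5. Which late SAEs lack a stated 24-hour duty.** Section 9.6 covers events considered caused by the product, 4.2 covers issues related or possibly related, 9.7 covers pregnancy complications and 9.9 covers medical emergencies. The statement in 9.5.1 that SAEs are reported whether or not drug related concerns causality and follows the sentence with the 30-day limit. The remainder is a late SAE judged unrelated and outside 9.7 and 9.9. The sponsor might first see it through eCRF review, which Section 13 places at regular intervals.

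**The case against.** **On the definition.** Experienced investigators will recognise the slip and treat admission as serious. The last bullet invites this: if events managed without admission can be serious, an admission seems serious all the more. Some admissions will meet the disruption criterion. Either the investigator or the sponsor may make the judgment, so the sponsor can classify a recorded admission as serious. An admission thought possibly related already triggers 24-hour notice to the Medical Monitor under 4.2. Section 11.4.3.1 also tabulates Grade 3 or 4, related and discontinuation events, so a severe admission would not disappear.

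All of this lessens the consequence, but it does not supply the missing criterion. Nothing obliges anyone to classify the admission as serious, and the other tables are not the SAE table.

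**On the windows.** Here the objection largely succeeds. Section 7.2.1 sets a minimum: it does not say that recording stops at 30 days. The opening of Section 7 sends its procedures to the time points in Section 8, where AE recording runs to Day 365 in every regimen. A site that follows Section 8 and the appendices satisfies every text. Sections 9.6 and 9.7 speak of an observation period and an SAE reporting period that can end before the trial does, so the 30 days in 9.5.1 can be read as a deliberately shorter expedited window. That reading is implied and nowhere stated, so a clarification is still worth making.

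**Conclusion.** The omission in 9.2.4 is an error as written, and should be fixed. A new admission that meets no other criterion may miss the 24-hour SAE report and the SAE table, on any study day. The size per event is as shown in the working; the number of events is unknown. This assumes that no document outside the protocol, such as the SAE form or the Study Manual, supplies the criterion.

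A reader might infer two stronger claims, and the documents support neither:

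- **That admissions would be lost from the safety data.** They would still be recorded as AEs; what is uncertain is the serious label.
- **That the 30-day wording cuts off safety capture for most of follow-up, so that late SAEs drop out of the analysis.** Section 8 and the appendix footnotes require recording to the end of study, so late SAEs reach the eCRF and the SAE table when those are followed. What remains is the speed of notification for late SAEs judged unrelated.

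The window point is a minor wording matter, and the conclusion on 9.2.4 does not depend on it.

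**What to change.** **Main change.** In the hospital bullet of 9.2.4, insert *inpatient hospitalization or* after the first word, so that new admission and prolongation are both criteria.

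**Clarification.** Align the 30-day sentences in 7.2.1 and 9.4.1 with the appendix window (the later of 30 days after the last dose and the end-of-study visit). In 9.5.1, state which applies: the 24-hour SAE duty ends at 30 days, or it runs to the end of study. If it is extended, check the period terms in 9.6 and 9.7 against it.

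**Cost.** One bullet and one sentence each in 7.2.1, 9.4.1 and 9.5.1, made through a written amendment with IRB approval (12.4, 14.2). The main change may bring a few more SAE reports. Extending the 24-hour duty would add some during follow-up, including unrelated events; stating the shorter window would add none. No visit, sample size or analysis method changes.
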